4 STUDY POPULATION

4.1 INCLUSION CRITERIA

- 9-17 years of age
- Sustained a concussion ≥ 6 weeks ≤ 16 weeks from date of ophthalmic exam
 - Criteria for concussion: clinically diagnosed by physician
- Best corrected visual acuity: 20/30 in both eyes at near; 20/25 in each eye at distance
- Minimum Stereopsis: 500" global
- CISS score ≥ 16
- Refractive error at least $\pm 0.50D$ sphere or cylinder
- Ability to clear ≥ 0.50 cycles per minute in monocular accommodative flipper of and binocular accommodative flipper

4.2 EXCLUSION CRITERIA

- Diplopia from nerve palsies
- Retinal pathology
- Significant co-morbid neurodevelopmental disorder (e.g. autism spectrum disorder, brain injury, documented neurogenetic disorder; known brain malformation)
- Intellectual/developmental delay
- Prior diagnosis of ADHD that is not adequately controlled with medication
- Previous treatment of any amount of bifocal lenses and base in prism since concussion
 - Vision therapy ≥ 6 weeks since concussion

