1 PROTOCOL SUMMARY

1.1 SYNOPSIS

Title:	Spectacle lenses in concussed kids
Study Description:	Many kids who have sustained a concussion still experience symptoms months after the event. This study will examine if certain types of lenses in glasses will help alleviate those symptoms.
Objectives:	Compare symptoms of concussed kids after wearing different types of glasses, one of which is a control.
Endpoints:	3 month follow up phone call
Study Population:	9-17 year olds who have sustained a concussion and are symptomatic
Phase:	3
Description of Study Intervention:	Different types of glasses lenses that are already commercially available and are used routinely in concussion patient.
Study Duration:	2-3 years, largely dependent on ability to recruit subjects
Subject Duration:	3 months

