1.2 SCHEDULE OF ACTIVITIES (SOA)

1. Participants are recruited through routine eye exams at concussion clinic
2. If a patient is eligible for study, an investigator will reach out to the patient at that time to present patient with the opportunity to enroll in the study. The patient has 1 week from that date to decide.
3. Once consents are signed and subject is officially enrolled, they will be randomized into 1 of 3 possible lens options.
4. Investigators will then order the lenses from the supplier to then be fit in patient's glasses
5. Dispense of glasses to participant (timing will vary due to dependence on supplier). Repeat concussion survey at dispense.

6. Masked in-person exam 4-6 weeks from dispense of glasses
 - a. Standard binocular vision assessment for primary and secondary measurements
7. Last assessment: 3 month phone call after dispense of glasses for last concussion survey

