2 INTRODUCTION

2.1 STUDY RATIONALE

The main goal for this study is to determine the effectiveness of anti-fatigue (low additional prescription at near) in treating post-concussion patients for their visual symptoms. The main outcome measurement will be the convergence insufficiency symptom survey (CISS) pre-intervention and post-intervention of the anti-fatigue lenses. This will be compared to the CISS results of single vision glasses (rule out placebo effects)

Other secondary outcome measurement will be objective measurements of vergence ranges and accommodation magnitude and flexibility, reduction of symptoms with single vision glasses alone for low refractive error individuals and the effects of anti-reflective coating.

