2.3.2 KNOWN POTENTIAL BENEFITS

It is possible that some of the patients might find resolution of symptoms depending on the treatment arm. The results of this research may change or help guide the treatment of concussion patients by providing evidence-based treatment results. Given the extensive costs related to concussion management and the cost of progressive addition lenses compared to typical glasses prescribed for children, this prospective project will help doctors and families make decisions on prioritizing treatment options following concussion.

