5 STUDY INTERVENTION

5.1 STUDY INTERVENTION(S) ADMINISTRATION

5.1.1 STUDY INTERVENTION DESCRIPTION

Different types of glasses lenses that are already commercially available and have been commonly used to treat concussion patients through anecdotal experience.

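### The prior-treatment exclusion in Section 4.2 does not name the trial's own test lens, so a child already wearing that lens type can enter as the rule is written

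*Protocol*

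**What the plan says.** Protocol Section 4.2 lists, as one exclusion, "Previous treatment of any amount of bifocal lenses and base in prism since concussion". Nested beneath it is "Vision therapy ≥ 6 weeks since concussion".

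Section 2.1 gives the aim: to "determine the effectiveness of anti-fatigue (low additional prescription at near) in treating post-concussion patients for their visual symptoms". The main outcome there is CISS before and after the intervention, compared with single vision glasses. Section 1.2 says children are "randomized into 1 of 3 possible lens options"; the three options are not itemised anywhere.

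On current use, the synopsis (1.1) describes the study lenses as "already commercially available and are used routinely in concussion patient", and Section 5.1.1 says they "have been commonly used to treat concussion patients through anecdotal experience".

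The other relevant rules are in Section 4.1 (exam 6 to 16 weeks after the concussion, CISS of at least 16) and Section 5.4 (no concomitant therapy, worded for the period of the study only).

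**The concern.** A rule that bars prior bifocals at any amount since the injury is evidently meant to keep out children whose near work has already been treated optically. Yet it leaves unnamed the one near add that the trial sets out to test, while the protocol says that lenses of this kind are already in everyday use for these patients.

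The main outcome is a change from a pre-treatment score. For a child already wearing a low near add, the score at entry is not pre-treatment. If randomised to the anti-fatigue lens, the child continues much as before. If randomised to single vision, the child loses the add, and the control arm records what happens on withdrawal. Neither is the comparison described in Section 2.1.

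The statistical analysis plan cannot settle this, because the wording decides who is enrolled.

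**Working it through.** No figure in the plan needs reproducing. The check sets the wording of the sections side by side, and then illustrates the size under stated assumptions.

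**1. Does any criterion cover prior wear of the test lens?** There are three ways to read the lens exclusion in 4.2:

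| Reading | Bifocals alone | Prism alone | Anti-fatigue lens |
|---|---|---|---|
| (a) *and* requires both treatments | eligible | eligible | eligible |
| (b) *and* joins two items, either of which excludes | excluded | excluded | eligible |
| (c) as (b), with bifocal stretched to mean any near add | excluded | excluded | excluded |

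Under (a) and (b) the test lens is not covered. Only (c) covers it, and the text does not say (c). Nothing else in 4.1 or 4.2 mentions prior near-add wear, and 5.4 does not reach back before enrolment.

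**2. Is prior wear plausible?** Sections 1.1 and 5.1.1 say the lenses are in use in this population, and there are 6 to 16 weeks between injury and exam in which they could be prescribed. No rate is given.

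**3. What would it do to the contrast?** Let p be the fraction of entrants already wearing a near add, D the add-versus-single-vision difference in untreated children, and D* the same difference among prior wearers. Randomisation makes p equal across arms in expectation, so the trial estimates

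(1 − p) × D + p × D*.

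- If prior wearers gain nothing further and lose nothing on single vision, D* = 0 and the result is (1 − p) × D. Assuming p = 0.10 gives 0.90 × D; assuming p = 0.30 gives 0.70 × D.
- If those moved to single vision worsen on losing the add by enough that D* exceeds D, the estimate exceeds D and flatters the lens.

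Of the 90 planned participants (3.2), those fractions are 0.10 × 90 = 9 and 0.30 × 90 = 27 children. Both p and D* are assumptions; the protocol gives neither.

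**4. The vision-therapy line.** It can mean a course lasting at least 6 weeks, or therapy given 6 or more weeks after injury. Take a child in week 5 of a course still running at the exam. On the first reading the course is too short to exclude. On the second the child is excluded, because 4.1 places every exam at least 6 weeks after the injury, so therapy still running then falls beyond the limit. The same child is classified in opposite ways.

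**The case against.** The strongest reply is that 4.2 is loosely worded but its intent is plain. Barring bifocals at any amount could be taken to mean any strength of near add, in which case the test lens is already excluded. That is a possible reading, but the text does not state it. The protocol calls its own lens something else, and the rule has to be applied at five sites (3.1) with a new resident each year (5.3).

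Several further objections stand and limit the point:

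- A reader might infer that a child treated with bifocals alone is definitely eligible. That needs a strictly conjunctive *and*. In an exclusion list the likelier intent is that either treatment excludes, so this is an ambiguity only.
- A reader might infer that progressive lenses are also a trial lens. They appear only in Section 2.3.2, in a remark on "the cost of progressive addition lenses compared to typical glasses prescribed for children", and the three options are never itemised. The anti-fatigue lens alone carries the point.
- Prior wear is plausible, but its frequency is unknown. Recruitment takes place at the concussion-clinic eye exam (1.2), which may be where such lenses are first prescribed.
- Randomisation applies to prior wearers too. They modify the effect; they do not confound the comparison.
- For vision therapy, length of course is arguably the ordinary reading, since the line sits under previous treatment. Section 5.4 would also stop an ongoing course during the study. It does not decide whether that child is eligible at entry.

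**Conclusion.** The point holds in a limited form. Section 4.2 does not exclude prior wear of the trial's own test lens unless bifocal is read more widely than it is written. A child already on that lens type can therefore enter with an on-treatment baseline and may then be withdrawn from the add by randomisation.

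The effect on the main contrast is unknown in size and direction. The 90% to 70% range rests on an assumed 10% to 30% of prior wearers and an assumed absence of any further response or withdrawal effect. A reader might conclude that the trial could then no longer answer the question in Section 2.1. The documents do not support that: the comparison remains randomised, 2.1 speaks of post-concussion patients without requiring that they be new to such lenses, and under the same assumptions most of the effect remains.

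The *and* and the vision-therapy line are ambiguities to be cleared up, not demonstrated gaps. Taken together this is a cheap improvement, not a flaw that by itself invalidates the trial.

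**What to change.** Reword the lens exclusion in Section 4.2 along these lines: *since the concussion, wear of any near-addition lens (bifocal, anti-fatigue or other near add), or any base-in prism*. This extends the existing zero-tolerance rule to the lens being tested and removes the doubt over *and*.

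Make vision therapy a separate bullet that says whether the 6 weeks is the length of the course or the time since injury. The sponsor should settle which. A blanket bar on vision therapy would be a new eligibility rule, which the ambiguity does not call for.

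The cost is a one-paragraph amendment and some added screen exclusions. Their number is unknown. On the illustrative 10% to 30%, the children excluded would be 9 to 27 of every 90 who would otherwise have entered, so the sponsor should weigh this against Sections 3.2 and 6.1, which name difficulty in enrolment as a reason to stop early. Asking about prior glasses should add little work, since the present exclusion already requires it.

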4.3 SCREEN FAILURES

If a participant is later excluded from the study, they would be notified.

4.4 STRATEGIES FOR RECRUITMENT AND RETENTION

Recruitment will be directly from the eye clinics of Boston Children's Hospital and the University of Alabama School of Optometry. Both clinics already have an established concussion clinic. We will provide patients with a \$5 gift card if they complete the study, although this may be site dependent depending on funding.

5 STUDY INTERVENTION

5.1 STUDY INTERVENTION(S) ADMINISTRATION

5.1.1 STUDY INTERVENTION DESCRIPTION

Different types of glasses lenses that are already commercially available and have been commonly used to treat concussion patients through anecdotal experience.

5.1.2 DOSING AND ADMINISTRATION

Dosing is the same throughout treatment arms. Participants are expected to wear the glasses regardless of treatment arm every day. This would be self-administrated.

5.2 MEASURES TO MINIMIZE BIAS: RANDOMIZATION

Randomization is done as participants are recruited using an excel formula.

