2.3 RISK/BENEFIT ASSESSMENT

2.3.1 KNOWN POTENTIAL RISKS

None. This study minimizes risk to the participant by using non-invasive procedures already being done as part of standard clinical eye care practice. Visual acuity, stereoacuity, ocular alignment, and other visual efficiency testing are done as part of standard practice. Unmasked investigators will be available to address these risks, allowing discontinuation of study treatment to pursue other interventions if needed. It is the investigator's opinion that the protocol's level of risk falls under DHHS46.404, which is research not involving greater than minimal risk. Although no adverse events are anticipated as a result of this treatment, all adverse events will be reported.

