3 STUDY DESIGN

3.1 OVERALL DESIGN

This is a multi-site clinical trial (Identifier: NCT03123822) including Boston Children's Hospital, Salus University Pennsylvania College of Optometry, [name] private practice, Akron Children's Hospital, and the University of Alabama at Birmingham (coordinating site). All sites have identical study designs: a prospective randomized group comparison observational study with a masked examiner to treatment arm.

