5.3 STUDY INTERVENTION COMPLIANCE

The study will be completed by a new resident each year but the PI will have direct oversight of the resident to ensure that the protocol is adhered to. Compliance of the device will be self-reported by the participant.

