6.2 SUBJECT DISCONTINUATION/WITHDRAWAL FROM THE STUDY

Subjects are free to withdraw from participation in the study at any time upon request.

An investigator may discontinue or withdraw a subject from the study for the following reasons:

- Significant study intervention non-compliance
- If any clinical adverse event (AE), laboratory abnormality, or other medical condition or situation occurs such that continued participation in the study would not be in the best interest of the subject

Subjects who sign the informed consent form and are randomized but do not receive the study intervention may be replaced. Subjects who sign the informed consent form, and are randomized and receive the study intervention, and subsequently withdraw, or are withdrawn or discontinued from the study, will not be replaced.

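### Allocation by an Excel formula run at recruitment has no locked sequence or draw record, and section 6.2 allows replacement after staff know the arm without saying how it is assigned or recorded

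*Protocol*

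**What the plan says.** Section 5.2, the protocol's section on measures against bias, consists of one sentence: "Randomization is done as participants are recruited using an excel formula". The Schedule of Activities (1.2) adds when this happens and the number of arms: "Once consents are signed and subject is officially enrolled, they will be randomized into 1 of 3 possible lens options". No allocation ratio is given.

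The same schedule then says "Investigators will then order the lenses from the supplier". It describes the dispensing date as one whose "timing will vary due to dependence on supplier", and no upper limit is stated. Section 3.1 describes a design "with a masked examiner to treatment arm". Section 2.3.1 refers to investigators who are not masked: "Unmasked investigators will be available to address these risks".

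On replacement, section 6.2 says "Subjects who sign the informed consent form and are randomized but do not receive the study intervention may be replaced". It then rules out replacing anyone who has received the intervention. The same section lists the grounds on which an investigator may withdraw a child: significant non-compliance, or an adverse event or other medical condition or situation that makes continuing against the child's interest. Section 6.3 asks for documented contact attempts and a primary reason when a child is lost to follow-up. Section 3.2 treats the study as finished at 90 enrolled.

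**The concern.** Two gaps act together.

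The first is the draw. A formula run at the time of recruitment produces a result that can be seen and, unless something prevents it, produced again. The protocol does not say who runs it, at which of the five sites, or where the result is written down. If a draw were repeated, no required record would show it.

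The second is the interval between draw and dispensing. Whoever orders the lenses knows the arm, and the wait is of unstated length. During that wait a child who ends up without lenses can be replaced. Section 6.2 does not say whether the replacement inherits the vacated assignment or gets a new draw, or whether the first child remains on the randomisation record.

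Either route could let a child's expected outcome influence who is counted in which arm. The main outcome is the CISS, a symptom survey, and masking the examiner does nothing to control who enters each arm. Section 5.3 says "The study will be completed by a new resident each year", so a safeguard that is not written down may not survive the handover, although the principal investigator does oversee the resident directly. Even with no bias at all, the trial as written could not show afterwards that its allocation was sound.

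**Working it through.** **Text check.** The protocol states no figure to reproduce on this point. The relevant provisions, side by side:

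| Question | What the protocol provides |
|---|---|
| Sequence fixed before enrolment? | Not provided for; 5.2 describes a formula used at recruitment |
| Who runs the formula, and where? | Not stated |
| Record of each draw? | Not stated; 9.1.4 and 9.1.5.1 cover source worksheets, CRFs and monitoring in general and mention neither randomisation nor replacement |
| Draw before or after consent and enrolment? | After (1.2) |
| Arm known to staff before dispensing? | Yes, through the lens order (1.2) |
| Replacement before dispensing? | Allowed (6.2) |
| How is the replacement assigned? | Not stated |
| Does the replaced child stay on record under the arm? | Not stated |
| Does the replaced child count toward the 90? | Not stated (3.2, 6.2) |

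**Illustration 1: repeated draw.** Assume three equally likely arms (the ratio is not stated). The chance of reaching a given arm within k draws is 1 − (2/3)^k. For k = 1 this is 33.3%, for k = 2 it is 1 − 4/9 = 55.6%, and for k = 3 it is 1 − 8/27 = 70.4%.

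**Illustration 2: selective replacement.** Assumptions, none of them from the protocol:
- the worst-prognosis fraction f of one arm is replaced in that arm by unselected children, and no other arm is touched;
- prognosis and outcome are normal with correlation r;
- 30 children per arm, i.e. 90 split equally;
- an unadjusted two-sided 5% t-test with 58 degrees of freedom.

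Removing the lowest fraction f and refilling it with average children shifts the arm mean by r·φ(z_f), in outcome SD units, where z_f is the f-quantile of the standard normal and φ its density. For f = 10%, z = −1.282 and φ(z) = 0.1755.

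- r = 0.3: shift 0.3 × 0.1755 = 0.053 SD
- r = 0.5: shift 0.5 × 0.1755 = 0.088 SD

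The noncentrality is shift × √(30/2) = shift × 3.873, and the critical value is 2.002.

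- r = 0.3: noncentrality 0.204, type I error 5.5%
- r = 0.5: noncentrality 0.340, type I error 6.3%

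Two variants of the mechanism, simulated at f = 10% and r = 0.3 to 0.5, give similar results. With replacements freshly randomised 1:1:1, the error is 5.5 to 6.7%. With the draw re-run once for each worst-10% child drawn to one arm, it is 5.6 to 6.4%.

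**Effect of baseline adjustment.** If selection acts through baseline CISS and the analysis adjusts for it, simulation with the lowest 3 of 30 replaced returns the error to about nominal (5.2% at r = 0.3 and 5.0% at r = 0.5, 20,000 trials). Selection on prognosis that is not measured would remain.

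**The case against.** The strongest reply is that this is mostly silence rather than error. An Excel formula can be a sound random generator, and a locked list may exist without being described. That stands as a limit: the protocol does not say that draws are repeated. But 5.2 does state a method, and its wording points to draws made at recruitment. How assignments are drawn and recorded is trial conduct, needed before the first child enters, and is not normally left to an analysis plan.

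A reader might infer more than the document supports, in four ways:

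- **That enrolling staff can foresee the next assignment.** Consent and enrolment come before the draw (1.2). If the draw is live and random, there is nothing to foresee at enrolment, so foreknowledge is not shown.
- **That 6.2 lets staff drop a child because of the arm.** It does not. Withdrawal by an investigator is limited to listed grounds, treated children are not replaced, and 6.3 requires a reason for loss to follow-up. These rules govern why a child leaves. They do not say how the replacement is assigned or whether the first child is kept on the allocation record.
- **That the yearly change of resident leaves allocation unsupervised.** Section 5.3 gives the principal investigator direct oversight to ensure adherence. The gap is that the protocol contains no allocation rule beyond the one sentence to adhere to.
- **That the absence of site stratification or blocking is part of the defect.** Neither would stop a re-run or a selective replacement. Both are design choices.

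It is also fair to say that the size calculation is a constructed scenario, needing selection in one arm and none in the others, and that the result is close to nominal when correlation is weak. It serves only as a scale.

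**Conclusion.** The point holds in a limited form. As written, the allocation is an at-recruitment formula with no locked sequence and no draw record, followed by an interval in which staff know the arm and replacement is allowed without a rule for assigning the replacement or retaining the first child on record. A repeated draw would leave no required trace.

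The bias is potential, and its size cannot be derived from the protocol, which gives no rate of re-drawing or replacement. Under the stated assumptions (worst 10% of one arm replaced, correlation 0.3 to 0.5, 30 vs 30, unadjusted test), the shift is about 0.05 to 0.09 SD and the type I error about 5.5 to 6.3%. It is less if selection runs through baseline CISS and the analysis adjusts for it. The document does not support concluding that the allocation was manipulated or that the result will be biased. The case for change rests on the trial being unable to demonstrate a sound allocation, and on how little the remedy costs.

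**What to change.** **Section 5.2.** Replace the formula run at recruitment with a list generated and locked before enrolment at the coordinating site. State the allocation ratio. Release each assignment through a time-stamped log, and only after consent, eligibility and baseline CISS are recorded. If such a list already exists, describing it here is enough.

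**Section 6.2.** State that a replacement takes the next entry on the list, that the replaced child stays recorded under the assigned arm with the reason, and whether that child counts toward the 90.

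Stratifying by site and varying the block size are optional and not needed to close this point.

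**Cost.** A few hours to generate and lock the list, one paragraph in 5.2 and one or two sentences in 6.2. No extra visits or children are needed. The downside is that sites must contact the coordinating site for each assignment.
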